9.5.6.8 Early Termination Visit

If a subject terminates the study before Day 29, every effort will be made to have the subject undergo the procedures as described in Section 9.5.6.4 for the follow-up visit.

In case an early termination visit as described above is not possible, a follow-up safety phone call should be made as soon as possible after termination to capture any SAEs or AESIs since the last study visit, if possible.

The reason for premature termination must be documented in the subject's medical records and in the eCRF.

9.5.7 Appropriateness of measurements

Standard safety assessment methods are used in this study and are very similar to procedures performed in all previously conducted clinical studies in which the E2477A challenge strain was used.

The purpose of the current study is to estimate the incidence of moderate and severe diarrhea among participants challenged with 4×10^9 cfu of the *E. coli* E24377A strain. This dose is planned to be used in a subsequent randomized, double-blind, placebo-controlled phase 3 vaccination and CHIM study. In order to meet this objective, all stools will be collected during in-patient period from immediately after E24377A administration on Day 1 through meeting discharge criteria and examined, weighed, and graded by the study staff using standard criteria.

9.6 Data quality assurance

This study will be conducted in compliance with the CSP, relevant Standard Operating Procedures (SOPs), Good Clinical Practice (GCP) and the applicable regulatory requirement(s).

The Principal Investigator will provide SBH with all data produced during the study from the scheduled study assessments. He/she ensures the accuracy, completeness, legibility, and timelines of the data reported to SBH in the eCRF and in all required reports.

9.6.1 Monitoring

The study site will be [REDACTED] overseeing monitoring activities at times agreed on by the Investigator. It is the function of the Monitor to ascertain that all aspects of the CSP are complied with and that the conduct of the study conforms to applicable regulatory requirements and established rules for GCP.

At the time of each monitoring visit, the Monitor will review the eCRFs to ascertain that all items have been completed and that the data provided are accurate and obtained in the manner specified in the CSP.

The Monitor will also check that the data in the eCRF are consistent with the clinical records (Source Data Verification) and that study results are recorded completely and correctly.

The Monitor will check on the reporting of SAEs, procedures for test product accountability and record keeping. For this purpose, the Monitor must be given direct access to clinical records, original laboratory data, etc., as far as these relate to the study and without jeopardizing subject integrity. eCRFs for all included subjects must be made available to the Monitor for review.

Further details are provided in a separate Monitoring Plan.

9.6.2 Audits and inspections

Authorized representatives of SBH or a regulatory authority, may perform audits or inspections at the research clinic, including Source Data Verification (SDV). The purpose of an audit or inspection is to systematically and independently examine all study-related activities and documents, to determine whether these activities were conducted, and data were recorded, analyzed, and accurately reported according to the protocol, ICH-GCP guidelines and any applicable regulatory requirements. The Investigator will contact SBH immediately if contacted by a Regulatory Authority about an inspection at the site.

9.6.3 eCase Report Forms (eCRFs)

An eCRF must be completed and signed by authorized personnel for each included subject, according to the eCRF completion instructions.

All data must be entered in English. The eCRFs should always reflect the latest observations made during the subjects' participation in the study. Therefore, the eCRFs should be completed as soon as possible during or after the subject's visit. Data generated during the inpatient period will be entered in a timely fashion after discharge of the volunteers.

The Investigator must verify that all data entries in the eCRFs are accurate and correct by signing the completed eCRF.

The completed eCRFs should be made available for checking of completeness and accuracy by the Monitor.

Please see Section 9.8 for further details.

9.6.4 Source Data

A separate source data document will be generated by the site before start of subject screening. The source documents will include all information appearing in the eCRFs.

The Investigator should guarantee access to source documents to the Monitor and Regulatory Authorities, if required.

9.6.5 Training of study staff

Before screening of the first subject the Monitor and/or Project Manager will perform an initiation visit at the study site. The requirements of the Clinical Study Protocol and related documents will be reviewed and discussed, and the study staff will be trained in any study specific procedures and system(s) utilized.

It is the responsibility of the Principal Investigator to ensure that all personnel involved in the study are fully informed of all relevant aspects of the study, and have a detailed knowledge of and training in the procedures that are to be executed by them, including good documentation practice. Any new information of relevance to the performance of this study must be forwarded to the staff involved in a timely manner.

The Investigator will keep a list of all personnel involved in the study together with their function and study related duties delegated. A Curriculum Vitae (CV) will be available for all CIR staff delegated study-specific duties.

9.7 Statistical methods and determination of sample size

A detailed statistical analysis plan (SAP) will be written and finalized in advance of database lock. The plan will follow the outline of the statistical analyses presented below, but details necessary to complete the statistical analyses will be given.

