9 INVESTIGATIONAL PLAN

This is an open label study with the aim to estimate the incidence of moderate and severe diarrhea among participants challenged with 4×10^9 cfu of the *E. coli* E24377A strain. [REDACTED]

The study will be conducted at one site; the Center for Immunization Research, Johns Hopkins Bloomberg School of Public Health in Baltimore, Maryland, United States.

Up to 30 (minimum 25) subjects will be enrolled and challenged with approximately 4×10^9 cfu of the *E. coli* E24377A strain.

Overall description of study design

The study will consist of three study periods: screening, inpatient period and outpatient follow-up. Subjects will be evaluated for study eligibility during the screening period. After provision of written informed consent, subject eligibility for study entry will be assessed. Subjects who have been assessed to be eligible for the study, based on screening evaluations, will be admitted to the in-patient unit on Day -1, the day before E24377A administration, for study orientation and to be monitored for any signs and symptoms of illness. At baseline (Day 1), subjects who remain eligible and are willing to participate will be enrolled in the study and receive a single administration of E24377A.

Subjects may remain in the in-patient unit until they meet discharge criteria, see Section 9.4.8.2. Routine discharge is scheduled for Day 9, dependent upon 2 consecutive negative stool culture results. During the in-patient period, subjects will be examined daily for signs and symptoms of ETEC illness. Vital signs will be measured at least 3 times daily starting on Day 1, and postural blood pressure and pulse will be measured as needed. All stools will be collected and evaluated, weighed, and graded by the study staff. Up to 3 stools and/or rectal swabs collected each day will be cultured.

If the subject develops any symptom suggestive of diarrhea, they will be encouraged to drink liquids. If a subject vomits or is unable to consume an adequate volume of liquids, then intravenous (IV) fluids may be administered.

In order to reduce the risk of secondary infection after discharge, all subjects will receive a 3-day course of antibiotics. The subject will begin a 3-day course of ciprofloxacin 500 mg by mouth twice daily (or azithromycin 500 mg by mouth daily for three days, or amoxicillin 500 mg by mouth three times daily for three days if the subject was allergic to or unwilling to take

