9.7.6.7 Interim analyses and data monitoring

An adjudication of challenge outcome data will be performed after completion of the in-patient period. Following a partial lock of the challenge outcome data, topline results will be generated before the last subject's follow-up contact.

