9.9.2 Entering of data into the eCRF

The eCRFs should always reflect the latest observations made during the subjects' participation in the study. The eCRFs should be completed as soon as possible during or after the subject's visit.

If some assessments are not done, or if certain information is not available, not applicable or unknown, this will be indicated in the eCRF.

Entries triggering internal eCRF checks will be presented as errors and warnings. Forms with incomplete entries or that contains triggered errors cannot be set to completed state.

The Investigator must verify that all data entries in the eCRFs are accurate and correct by signing the completed eCRF.

Once all data have been entered, verified, and validated, the database will be locked.

After the eCRF has been locked, the data will be sent to the Sponsor and a copy to the research clinic to be filed in the Investigator Study File (ISF) for archiving.

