11.2 Study timetable

The end of the study is defined as the last follow-up contact of the last subject participating in the study.

The study is expected to start in Quarter 1, 2024 and it is expected be completed by Quarter 3 2024.

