**Statistical Analysis Plan**

SPONSOR: Scandinavian Biopharma Holding AB (SBH)	PROTOCOL NUMBER: OEV-131	PROTOCOL TITLE: Pre-Study of wild type Enterotoxigenic E.coli (ETEC) Strain for Verification of a planned Challenge Dose	VERSION NO: 1.0
			VERSION DATE: 14JUN2024

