### 2.4.3. Blinding

Not applicable, as this is an open label study.

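### The SAP is due only before database lock, but this open-label study adjudicates and reports its primary result on an earlier partial lock, so rules found only in the SAP can be set or changed with outcomes known

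*Protocol*

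**What the plan says.** **Deadline.** Protocol 9.7 states: "A detailed statistical analysis plan (SAP) will be written and finalized in advance of database lock". It names no other milestone. Protocol 9.9.2 describes the lock: "Once all data have been entered, verified, and validated, the database will be locked".

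**Read-out.** Protocol 9.7.6.7 places the primary result earlier: "An adjudication of challenge outcome data will be performed after completion of the in-patient period", and "Following a partial lock of the challenge outcome data, topline results will be generated before the last subject's follow-up contact". SAP 8.1 gives the sequence as partial lock, listings for the committee, adjudication, then topline. It includes the primary endpoint in topline and treats those results as final although follow-up continues.

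**Masking.** Protocol 9 says "This is an open label study", and SAP 2.4.3 says "Not applicable, as this is an open label study". Under Protocol 9.5.3.1 all stools are collected, weighed and graded during the in-patient stay.

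**Dates.** The SAP title block reads "VERSION DATE: 14JUN2024", and the revision history lists version 1.0 as the initial plan. Protocol 7.3.2 plans enrolment, which is also the day of challenge, in the first quarter of 2024. Protocol 11.2 ends the study at the last subject's last contact and says "it is expected be completed by Quarter 3 2024".

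**The concern.** Finalising a SAP before database lock protects a blinded trial because no one can relate an analysis choice to a result until then. Here nothing is masked. Stool counts and weights are visible as they arise, the committee's decisions follow the partial lock, and the topline report follows those decisions. A SAP written or revised after all of that would still comply with Protocol 9.7.

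The study exists to estimate an attack rate at the dose planned for a later phase 3 challenge trial. It has no hypothesis test and the supplied text sets no success threshold, so type I error is not at issue. What is at stake is whether the report can show that its analysis rules were chosen without reference to the outcomes.

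**Working it through.** **1. Is the planned timetable consistent with itself?** Challenge is Day 1, so Day k = challenge date + (k − 1) days. If the last challenge is on 31 March 2024 (end of the planned enrolment quarter), Day 180 = 31 March + 179 days = 26 September 2024. That lies in the third quarter, so the stated completion quarter is reproduced.

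**2. Latest challenge compatible with completion by 30 September 2024.** Protocol 9.5.6.5 sets the final contact at Day 180 ± 14, that is Day 166 to Day 194. Latest challenge = 30 September 2024 − (k − 1) days. The gaps run to the SAP date of 14 June 2024. The end of the 120-hour window is challenge + 5 days, and Day 9 is challenge + 8 days.

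| Basis | Latest challenge | SAP after challenge | After 120-hour window | After routine Day 9 |
|---|---|---|---|---|
| Final contact at Day 166 (−165 days) | 18 April | 57 days | 52 days | 49 days |
| Final contact at Day 180 (−179 days) | 4 April | 71 days | 66 days | 63 days |
| Final contact at Day 194 (−193 days) | 21 March | 85 days | 80 days | 77 days |
| Enrolment ends 31 March | 31 March | 75 days | 70 days | 67 days |

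Each row uses the latest possible challenge date, so each gap is a minimum on that basis. The 49 days comes from the most lenient row. In reverse, a subject challenged on 14 June 2024 could not reach even Day 166 before 26 November 2024, which is outside the planned period.

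**3. What was already fixed outside the SAP?**
- Protocol 8.1.1 and 9.7.2: the stool thresholds, the 120-hour window, adjudication, and a two-sided 95% interval.
- Protocol 9.7.5.1: the Full Analysis Set.
- Protocol 9.5.3.1.3: the severity-score table, which SAP Table 2 repeats.
- Protocol 8.2.1: the two time-to-event endpoints.
- Protocol 9.8: an adjudication charter due before the in-patient period.

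**4. What appears first in the SAP?**
- *Missing data.* Protocol 9.7.6.2 defers this to the SAP. SAP 3.5 then specifies no imputation.
- *Interval method.* SAP 3.1.1 names Clopper-Pearson; Protocol 9.7.2 names no method. For 18 of 25 subjects the 95% interval is (0.506, 0.879) by Clopper-Pearson, (0.524, 0.857) by Wilson and (0.544, 0.896) by Wald.
- *Unadjudicated sensitivity analysis.* SAP 2.5.3.
- *Event times for subjects adjudicated positive below the stool thresholds.* SAP 2.5.4.1 uses the time of antibiotic administration, with 120 hours as a sensitivity analysis.
- *Censoring.* SAP 2.5.4.3 censors subjects without diarrhea at 120 hours; the Table 15 footnote censors them at discharge. For the primary endpoint, SAP 2.5.4.1 censors at 120 hours; the same footnote uses 120 hours or discharge, whichever is first. An early discharge alters the risk set before 120 hours, and a later one alters it afterwards.

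Table 15 is marked for the topline report, so the censoring conflict must be settled for that report. Protocol 9.7 would allow it to be settled afterwards.

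**The case against.** The strongest reply is that little of consequence was left open. The primary definition and analysis set are in the protocol. Protocol 9.7 adds that the SAP will follow the outline given there. Case status is decided by committee vote under a charter due before the in-patient period. The event times in SAP 2.5.4.1 affect only a secondary Kaplan-Meier analysis, and the unadjudicated analysis applies the protocol's own thresholds and is labelled a sensitivity analysis. Even the interval method may have been intended early: for 15 of 25, Clopper-Pearson gives (0.387, 0.789), matching the (0.39, 0.79) in Protocol 9.7.5.2, whereas Wilson gives (0.407, 0.766) and Wald (0.408, 0.792). All of this stands, and it limits the point to the list in step 4 of the working.

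Three stronger readings are tempting and not supported.
- *That the SAP was written with the results in hand.* The dates are planned quarters. No actual challenge, adjudication or partial-lock date is given, and SAP 8.1 describes those steps in the future tense.
- *That SAP rules could move the attack rate by one subject's weight at a time.* No listed rule is shown to decide a subject's status. Only missing-data handling could bear on the point estimate, and the SAP expects missing data to be minimal.
- *That the SAP introduced the disease scoring.* The table is the protocol's. The SAP adds detail, such as one score per subject from the maximum of each component.

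The reply does not touch the deadline itself, which needs no assumption about dates: a SAP finalised after topline would comply with Protocol 9.7.

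**Conclusion.** The point holds in a limited form. The deadline in Protocol 9.7 falls after the event it should precede, and open-label conduct leaves no masking to make up for it. If the planned quarters held, SAP version 1.0 followed every challenge by at least 57 days, every 120-hour window by at least 52 days, and every routine Day 9 discharge by at least 49 days. Those figures rest on estimated dates and do not show that the SAP followed the partial lock or that anyone used outcome data.

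The exposure covers missing-data handling, the interval method, the unadjudicated sensitivity analysis, event times for below-threshold cases, and censoring. The charter was not among the documents, so it may already govern below-threshold cases and reduce this further. No change in the attack rate is shown. The consequence is that the report could not demonstrate that these rules were chosen independently of the outcomes.

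**What to change.** 1. Amend Protocol 9.7 so that the SAP, and any later version, is approved before the partial lock and the adjudication meeting, and ideally before the first challenge. If those steps have already happened, the new deadline can govern only what remains, and item 3 becomes the main safeguard.
2. Before that point, give one censoring rule for each time-to-event endpoint and use it in SAP 2.5.4 and in the Table 15 footnote.
3. In SAP 8.1, state the dates of first and last challenge, charter approval, SAP approval and partial lock. Label any analysis rule added after challenge that is in neither the protocol nor the charter. If the SAP preceded the outcomes, the same paragraph will show it.

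Reporting of the primary result needs no change, since SAP 5.1 and Table 12 already present the adjudicated endpoint defined in the protocol.

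The cost is one protocol sentence, one corrected censoring rule per endpoint and one dated SAP paragraph, with no extra data. The downside is that some secondary or sensitivity rules may have to be labelled as added after challenge.

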9.7.1 Demographics and baseline characteristics

9.7.1.1 Demographics

Descriptive statistics of demographics and other baseline characteristics will be presented.

9.7.1.2 Medical history and concomitant medication

Descriptive statistics of medical history, prior/concomitant medications, and on-study antibiotic treatment will be presented.

9.7.2 Analysis of Clinical and Microbiology endpoints

For the primary endpoint, the proportion of subjects with moderate and severe diarrhea (defined as ≥ 4 grade 3-5 stools **or** > 400 grams of grade 3-5 stools passed in a rolling 24-hour period), deemed attributable to ETEC by an adjudication committee, will be presented with point estimate and the corresponding two-sided 95% confidence interval. For secondary clinical and microbiology endpoints, descriptive statistics will be presented, including two-sided 95% confidence intervals where applicable. For time to event analysis (time to onset of diarrhea and time to primary endpoint) Kaplan-Meier time to event methods will be used.

9.7.2.1 Analysis of requirement for early antibiotic treatment

The number and percentage of subjects requiring early antibiotic treatment, defined as treatment beginning prior to Day 6, will be presented.

9.7.3 Analysis of safety

9.7.3.1 Adverse Events

AEs and SAEs will be recorded from administration of the challenge strain until the follow-up visit on Day 29. At the follow up contact (phone call) approximately 6 months after challenge, new SAEs, new chronic illnesses (capture new diagnoses e.g. diabetes, hypertension, cancer) and AESIs (see Section 9.5.2.1.1) will be queried, and any open AEs and/or expected events will be followed up.

AEs will be coded using the current Medical Dictionary for Regulatory Activities (MedDRA) and summarized by Preferred Term (PT) and System Organ Class (SOC). The number of subjects reporting AEs, and the number of AEs reported will be presented. The events will be tabulated by SOC, PT and by severity and relationship to test product. AEs leading to study withdrawal and SAEs will also be presented in separate tabulations.

9.7.3.2 Vital signs and Physical examination findings

Key vital signs (those measured on Day -1 and 30 minutes after challenge) will be summarized.

9.7.4 Analysis of exploratory assessment

The exploratory assessments will be reported separately from the Clinical Study Report (CSR).

9.7.5 Analysis data sets

9.7.5.1 Full Analysis Set (FAS)

Unless otherwise stated, all statistical evaluations will be based on all subjects who have been challenged with E24377A (regardless if the whole intended challenge dose was ingested or a subject vomited just after ingestion) and have available data.

9.7.5.2 Determination of sample size

In preparation for a planned phase 3 vaccination and CHIM study, it is assumed based on previous clinical experience, see Table 2 and Table 3 [18, 24] that a pre-study in up to 30 subjects should be sufficient to estimate the incidence of moderate and severe diarrhea among participants challenged with 4×10^9 cfu of the *E. coli* E24377A strain. With 25 subjects and an attack rate of 60% or 70%, the 95% confidence interval for the estimated incidence would be (0.39, 0.79) or (0.45, 0.87), respectively.

Since there is a maximum capacity of 30 subjects for the in-patient period, the number of subjects will not exceed 30.

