9.3.4 Number of subjects

Up to 30 (minimum 25) healthy subjects will be enrolled in the study. Since there is a maximum capacity of 30 subjects for the in-patient period, the number of subjects who receive the

Confidential

28 (67)

Template Version:30MAR2020

(App 1 SOP EtC1011)

E24377A strain will not exceed 30; however, additional alternate subjects may be recruited to fill in for subjects who are ineligible or chose to leave prior to challenge receipt.

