## 2.4. Statistical Considerations for the Study Design

### 2.4.1. Sample Size Considerations

In preparation for a planned phase 3 vaccination and CHIM study, it is assumed based on previous clinical experience, that a pre-study in up to 30 subjects should be sufficient to estimate the incidence of moderate and severe diarrhea among subjects challenged with 4x109 cfu of the *E. coli* E24377A strain. With 25 subjects and an attack rate of 60% or 72%, the 95% Clopper-Pearson confidence interval for the estimated incidence would be (0.39, 0.79) or (0.51, 0.88), respectively.

Since there is a maximum capacity of 30 subjects for the in-patient period, the number of subjects will not exceed 30.

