### 3. GENERAL STATISTICAL CONSIDERATIONS

#### 3.1. General Analysis Specifications

##### 3.1.1. Global Analysis Principles

The following general analysis principles will be applied unless otherwise specified:

Continuous variables will be summarized using the following descriptive statistics: n (non-missing sample size), mean, standard deviation, median, maximum, and minimum. Confidence intervals for means will be calculated via Student's t distribution. Categorical variables will be summarized as counts and percentages (based on the non-missing sample size). Exact binomial confidence intervals for percentages will be calculated using Clopper-Pearson methodology.

All tables will be annotated with the total number of subjects relevant to that table.

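### The protocol's 95% interval for a 70% attack rate in 25 subjects, (0.45, 0.87), cannot be reproduced: the lower limit is about 0.035 too low, a minor error that understates precision

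*Protocol*

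**What the plan says.** Protocol section 9.7.5.2 argues from earlier challenge studies (Tables 2 and 3) that up to 30 subjects should be enough to estimate the incidence of moderate and severe diarrhea. It then illustrates precision for 25 subjects at attack rates of 60% and 70%: "the 95% confidence interval for the estimated incidence would be (0.39, 0.79) or (0.45, 0.87), respectively". It names no interval method. Section 9.3.4 sets the range: "Up to 30 (minimum 25) healthy subjects will be enrolled in the study". The upper figure comes from the capacity of the in-patient unit.

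SAP section 2.4.1 repeats the statement with a different second scenario and names the method: "With 25 subjects and an attack rate of 60% or 72%, the 95% Clopper-Pearson confidence interval". The limits printed there are (0.39, 0.79) at 60% and (0.51, 0.88) at 72%. The 60% interval is the same as in the protocol. The 70% case has become 72%, and the SAP does not remark on the change.

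For the analysis itself, protocol section 9.7.2 says the primary proportion "will be presented with point estimate and the corresponding two-sided 95% confidence interval", and SAP section 3.1.1 fixes the method: "Exact binomial confidence intervals for percentages will be calculated using Clopper-Pearson methodology".

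**The concern.** Two features of the protocol's sentence invite a check.

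- **The widths run the wrong way.** The printed 70% interval is 0.87 − 0.45 = 0.42 wide, and the 60% interval is 0.79 − 0.39 = 0.40 wide. With n fixed, an interval for a proportion should narrow as the rate moves away from 50%.
- **70% of 25 is 17.5 subjects.** No observed result can equal it, so it is unclear which count the interval describes.

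The study estimates a single proportion and plans no formal test, so these intervals are how the protocol expresses what 25 subjects can deliver. The lower limit tells a reader how low the true attack rate could plausibly be when the dose is considered for the phase 3 challenge study. The 70% case is also a natural one to look at. Table 3 lists 7 of 10 (70%) for the earlier group at the planned dose, although that rate counts moderate to severe ETEC illness, which is broader than this study's endpoint.

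**Working it through.** **Inputs.** n = 25 and rates of 60% and 70% (protocol 9.7.5.2); rate of 72% (SAP 2.4.1); two-sided 95% confidence (protocol 9.7.2); Clopper-Pearson (SAP 2.4.1 and 3.1.1).

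**Formula.** For x events in n subjects, with B(q; a, b) the q-quantile of the beta distribution:

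- lower limit = B(0.025; x, n − x + 1)
- upper limit = B(0.975; x + 1, n − x)

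**Step 1: the companion figure.** 60% of 25 is x = 15. Lower = B(0.025; 15, 11) = 0.387 and upper = B(0.975; 16, 10) = 0.789. This rounds to the printed (0.39, 0.79), so the protocol's 60% figure is Clopper-Pearson.

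**Step 2: the 70% figure by the same method.** 0.70 × 25 = 17.5. The formula accepts a fractional x, so the table shows it beside the two neighbouring counts.

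| Count | Rate | Clopper-Pearson 95% | Rounded | Width |
|---|---|---|---|---|
| 15/25 | 60% | 0.387 to 0.789 | (0.39, 0.79) | 0.402 |
| 17/25 | 68% | 0.465 to 0.851 | (0.46, 0.85) | 0.386 |
| 17.5/25 | 70% | 0.485 to 0.865 | (0.49, 0.87) | 0.380 |
| 18/25 | 72% | 0.506 to 0.879 | (0.51, 0.88) | 0.373 |
| Protocol, 70% | 70% | not given | (0.45, 0.87) | 0.42 |

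(The lower limit for 17/25 is 0.464999 before rounding, hence 0.46.)

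The printed upper limit of 0.87 agrees with 17.5/25. The printed lower limit does not: 0.485 − 0.45 = 0.035. The width should be 0.38, and it should be smaller than the 60% width (0.402 falling to 0.380).

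**Step 3: other methods at n = 25.** These were Wald (normal, t and continuity-corrected), Wilson with and without continuity correction, Agresti-Coull, Jeffreys, uniform-prior beta, logit, arcsine and likelihood ratio, plus mid-p and Blaker at whole counts. None gives (0.45, 0.87) at 17, 17.5 or 18. The smallest lower limit found is 0.4645 (Wilson with continuity correction, 17/25). At 17.5 the lower limits run from 0.484 (continuity-corrected Wilson) to 0.520 (Wald).

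**Step 4: a different n or confidence level.**

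- No whole count with n from 15 to 40 gives the pair by any method searched (all of the above except Blaker).
- If a fractional count of exactly 70% is allowed, a few non-exact methods reach the pair at n = 15 to 17, for example Wilson at 10.5/15 (0.448, 0.870). The protocol states 25 subjects, so these do not explain the figure.
- Seven error levels from 0.01 to 0.10 were tried at n = 25 with Clopper-Pearson and Wald. None gives the pair.

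**Step 5: the SAP figure.** 18/25 gives (0.506, 0.879), which rounds to the printed (0.51, 0.88). It reproduces.

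**The case against.** The strongest reply accepts the arithmetic and disputes the weight. Most of it stands.

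- **The error is conservative.** The correct lower limit, about 0.49, makes the design look better.
- **The less favourable scenario is right.** Of the protocol's two cases, 60% has the wider correct interval (0.402 against 0.380), and it is stated correctly. A reader might infer that the whole precision argument for the sample size fails. It does not. One of two figures is wrong, the section also relies on earlier clinical experience, and the maximum of 30 is set by unit capacity.
- **Nothing downstream uses the figure.** The documents contain no threshold, go/no-go rule or test tied to this limit, and the SAP fixes Clopper-Pearson for the reported intervals.
- **The SAP does not state a rival precision for the same scenario.** A reader might set 0.45 against the SAP's lower limit (0.506 before rounding) and report an error of 0.056. That compares a 70% rate with a 72% rate. At 60%, the scenario they share, the two documents agree.
- **The fractional count is not a second error.** A planning rate need not be attainable, and the formula accepts 17.5. The non-integer does not cause the wrong lower limit. It does make the interval harder to check, and 18/25 avoids that.

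What the reply does not do is rescue the figure. Neither document gives a method or input that yields (0.45, 0.87), and the SAP changes the scenario without saying the protocol's number was wrong.

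**Conclusion.** The interval (0.45, 0.87) in protocol section 9.7.5.2 is wrong as written. Taken like for like (Clopper-Pearson, 17.5/25), the lower limit is about 0.035 too low and the width is 0.42 where 0.38 is correct, so precision is understated. It is one of two precision figures offered in support of the sample size, and the other is correct. The analysis, the enrolment range and every decision rule in the documents are unaffected. Severity: minor.

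This assumes that the protocol meant Clopper-Pearson for both intervals. It does not say so, but the 60% figure and the SAP both point to it. That no standard method works at n = 25 does not depend on that assumption. A slip in one digit of the lower limit would fit the matching upper limit, but the documents cannot confirm the cause.

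**What to change.** In protocol section 9.7.5.2, replace the second scenario with the one in SAP section 2.4.1, 18/25 = 72% with 95% interval (0.51, 0.88), and name the Clopper-Pearson method. The two documents then agree and both scenarios are attainable counts.

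Optionally, add the planned maximum of 30 subjects, where both 60% and 70% are whole counts: 18/30 gives (0.41, 0.77) and 21/30 gives (0.51, 0.85). This is useful to a reader but is not needed to correct the error.

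The cost is one sentence at the next protocol amendment, or a note to file. Conduct, data collection and analysis do not change.
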